4.11 Study Subject Replacement

Three subjects within a dose level must be observed during DLT evaluation period (defined as the 2 week pre-induction phase and the 7 weeks of induction phase) before accrual to the next higher dose level may begin. Evaluable subjects for DLT will be those who receive the pre-induction (week -2) dose of pembrolizumab. Inevaluable subjects (those who are registered but never receive the pre-induction dose of pembrolizumab) will be replaced.

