4.2.2 Pembrolizumab

Pembrolizumab treatment will start two weeks prior to BCG administration (week -2). Patients will receive three instillations of pembrolizumab concomitant with BCG (weeks 0, 2, and 4; induction period), followed by maintenance pembrolizumab (see duration of therapy; section 4.7). The dose that subjects receive will depend upon the cohort to which they are enrolled; the starting dose will be 1 mg/kg. Each pembrolizumab dose will be diluted in 50ml of sterile normal saline and injected into the bladder through sterile urethral catheterization during 1 or 2 minutes and retained for 2 hours. During the days that BCG and pembrolizumab are given concomitantly, BCG will be administered and immediately followed by pembrolizumab administration; each medication will be diluted in 50ml and the total volume of 100ml will be retained for 2 hours. If pembrolizumab administration is scheduled on the same day as the cystoscopy (weeks 17,

NU Study Number: NU 15U06
Merck Study Number: 3475-265

25, 33, 41, and 49), pembrolizumab may be injected through the cystoscope provided no abnormal findings were noted.

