4.3 Dose Escalation Scheme

There will be no dose escalation for BCG (patients on all cohorts will receive the same dose). The table below summarizes the pembrolizumab dose levels; subjects will receive the same dose of pembrolizumab during pre-induction, induction and maintenance phases. No dose reductions are permitted for pembrolizumab. BCG may be reduced for toxicity as described in section 4.4. A standard “3+3” dose escalation design will be utilized. Initially, the study will enroll 3 subjects at the starting dose (level 1), after which enrollment will be temporarily suspended until all 3 patients complete the DLT evaluation period (defined as the 2 week pre-induction phase and the seven weeks of induction phase). Once all 3 subjects complete the DLT period and toxicity data has been reviewed by the Northwestern University Data Monitoring Committee, a decision will be made to proceed with escalation accordingly the rules below.

Table 4-2: Escalation Dose Levels			
Dose Level	Pembrolizumab	BCG	Number of patients
1	1 mg/kg	50mg	3-6
2	2 mg/kg	50mg	3-6
3	5 mg/kg	50mg	3-6
4	10 mg/kg	50mg	3-6

The following rules will be used at each dose level to determine whether or not to proceed to the next dose level:

- If 0 of 3 subjects at a given dose level experience a DLT (defined below), then escalation will proceed to the next dose level.
- If 2 or 3 of 3 subjects at a given dose level experience a DLT, then one of the following must occur:
 - If this happens at level 1, the study will be closed to further accrual and the regimen of pembrolizumab + BCG will be considered too toxic at any dose.
 - If this happens at level 2 or beyond, the previous level will be declared the maximum tolerated dose (MTD).
- If 1 of 3 subjects at a given dose level experiences a DLT, then an additional 3 slots will be added (for a total of 6 patients at that level):
 - If 1 of 6 total experiences a DLT, then escalation will proceed to the next level.
 - If ≥ 2 of 6 total experience a DLT, the previous level will be declared the MTD.

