NOTE: Whichever dose level is declared the MTD must have 6 total subjects treated at that level. For example, if 3 subjects are treated at level 2 and 0 subjects experience DLT, escalation would then proceed to level 3. However, if ≥ 2 subjects at level 3 experience DLT, enrollment to level 2 would need to be re-opened to enroll an additional 3 subjects at that level (with 0 or 1 DLT observed in 6 total subjects) in order to declare level 2 the MTD. If dose level 3 is achieved without MTD-defining DLT, dose level 3 will be considered the recommended phase II dose for future trials.

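### Section 4.11 makes a patient DLT-evaluable on one pembrolizumab dose given before any BCG, and replaces only never-dosed patients, so unobserved or BCG-unexposed patients can count toward escalation and the MTD

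*Combined protocol and SAP*

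**What the plan says.** Section 4.11 sets the denominator for the dose decision: "Evaluable subjects for DLT will be those who receive the pre-induction (week -2) dose of pembrolizumab". It also sets the replacement rule: "Inevaluable subjects (those who are registered but never receive the pre-induction dose of pembrolizumab) will be replaced". The same section opens with a further condition, "Three subjects within a dose level must be observed during DLT evaluation period". That period is two weeks of pre-induction plus seven weeks of induction, nine weeks in all. Section 4.2.2 places the first BCG two weeks after the qualifying dose.

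Section 4.3 allows the escalation decision "Once all 3 subjects complete the DLT period and toxicity data has been reviewed by the Northwestern University Data Monitoring Committee". The enrolment pause in that paragraph is written for the starting level. A level may be extended from three patients to six, or re-opened after a higher level fails, and "Whichever dose level is declared the MTD must have 6 total subjects treated at that level".

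Section 4.1 also treats one dose as enough for toxicity. It does contain a minimum-exposure condition: six BCG doses, three pembrolizumab doses, and safety data sufficient to assess DLTs. It applies that condition to response evaluability only.

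Section 4.3.1 covers missed treatment only as a delay of more than two weeks due to toxicity. Section 4.10 foresees consent withdrawal without follow-up and loss to follow-up, and attaches no DLT rule to either. Section 9 gives escalation probabilities of 91%, 49% and 17% at true DLT rates of 10%, 30% and 50%, and allows 27 enrolled for 24 evaluable.

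**The concern.** The primary outcome is the MTD of pembrolizumab given with BCG, and each level is judged on three to six patients. Under 4.11 a patient enters that count before receiving any of the combination. Two separate problems follow.

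- **Missing observation.** A dosed patient who withdraws consent or is lost during the nine weeks is evaluable and not replaced under 4.11. That patient cannot meet the observation sentence of 4.11 or the completion condition of 4.3. No section resolves this.
- **Missing exposure.** A patient who stops treatment for a non-toxicity reason but stays in follow-up can reach the end of the window by calendar. Both 4.3 and 4.11 are then met literally. The patient counts as DLT-free for a combination not received, or received only in part.

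Exposure matters on the protocol's own account. Section 7.2.8 says irritative effects of BCG usually appear after the third instillation and that reactions progress with later ones. The third instillation is at week 2, four weeks into the nine.

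Counting such a patient as a non-DLT can only lower the observed DLT count. Any error is therefore toward escalating or toward confirming a level as the MTD.

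**Working it through.** **Inputs.** The escalation rule is 0 of 3, or 1 of 3 followed by 0 of the 3 added (Section 4.3). True DLT rates p are 10%, 30% and 50% (Section 9). The share of DLT risk that a leaver retains and the early-exit rate d are not in the documents; both are assumptions shown over a range.

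**1. The plan's own figures.** P(escalate) = (1−p)³ + 3p(1−p)² × (1−p)³.
- p = 0.1: 0.906
- p = 0.3: 0.343 + 0.441 × 0.343 = 0.494
- p = 0.5: 0.172

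These match 91%, 49% and 17%. The formula gives every counted patient the full-window risk p.

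**2. One leaver scored as a non-DLT.** Let r be the leaver's remaining DLT risk.
- Among the first three: P(0) = (1−r)(1−p)² and P(1) = r(1−p)² + (1−r)·2p(1−p). Then P(escalate) = P(0) + P(1)(1−p)³. For p = 0.3 and r = 0: 0.49 + 0.42 × 0.343 = 0.634.
- Among the added three: P(escalate) = (1−p)³ + 3p(1−p)² × (1−p)²(1−r). For p = 0.3 and r = 0: 0.343 + 0.441 × 0.49 = 0.559.

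| Case | p = 10% | p = 30% | p = 50% |
|---|---|---|---|
| All fully exposed | 90.6% | 49.4% | 17.2% |
| One of first three, r = 0 | 94.1% | 63.4% | 31.3% |
| One of first three, r = p/2 | 92.4% | 56.4% | 24.2% |
| One of added three, r = 0 | 92.6% | 55.9% | 21.9% |
| One of added three, r = p/2 | 91.6% | 52.7% | 19.5% |

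**3. Confirming a re-opened level after 0 of 3.** At most 1 DLT in the new three is needed. With all three exposed the chance is 97.2/78.4/50.0%. With one at r = 0 it is 1−p², or 99.0/91.0/75.0%. With one at r = p/2 it is 98.1/84.7/62.5%.

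**4. Average effect.** If each patient leaves early with probability d and no DLT is seen, p becomes p(1−d). If half the risk is retained, p becomes p(1−d/2). At an assumed d = 5%:
- no retained risk: 91.4/52.5/20.2%, a shift of 0.8, 3.1 and 3.0 points;
- half retained: 91.0/51.0/18.6%, a shift of 0.4, 1.5 and 1.4 points.

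**5. Room for replacements.** The four-level rules were simulated, 100,000 trials per profile, with six patients required at the MTD. The five DLT profiles were equal 10%, 20% and 30%; 5/10/20/30%; and 10/20/30/50%. All 24 evaluable patients were needed in 0.8 to 1.4% of trials. The mean was 9 to 16 and the 95th percentile 21 or fewer. More than 18 were needed in about 4 to 11%, before any replacement.

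**The case against.** The strongest reply is that most of this is already handled.

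- **Section 4.3 asks for completion of a period in weeks, not of a number of doses.** Most exits in 4.10 permit follow-up, and the notes to Table 5 move leavers straight into it. This stands. A reader might infer that any early exit freezes a cohort. The documents do not support that: the conflict is confined mainly to consent withdrawal and loss to follow-up. The missing BCG exposure remains.
- **Three observed and six assessed are implicit in a standard 3+3.** A DLT is by definition an event in the nine-week window, so 1 DLT in 6 presupposes six patients assessed over it. This is fair. The lack of a repeated completion condition for the added three or a re-opened level is not a second defect. It is still worth writing down, because 4.11 defines evaluability otherwise.
- **Toxicity-driven exits are largely DLTs already**, through the rules on delays over two weeks and on Grade 2 events over ten days. Urinary frequency and urgency never count as DLTs. A DLT related to either drug counts, so a leaver keeps some risk. All of this stands, and it is why the zero-risk rows are an extreme.
- **Follow-up and committee review.** Adverse events are recorded to 30 days after treatment, and serious events and events of clinical interest to 90 days. The Data Monitoring Committee sees the toxicity data. Follow-up does not supply BCG exposure, and consent withdrawal ends it. The committee has no written rule for this patient and would have to settle the question after seeing the data.
- **The average effect is small.** It is, as step 4 shows.

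**Conclusion.** The point holds and should be fixed. Section 4.11 states a rule whose effect is that an unobserved patient, or one without BCG exposure, can stand in the denominator for escalation and for the MTD.

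The size depends on the frame. Within a cohort that has one such patient, the chance of escalating at a true DLT rate of 30% rises from 49.4% to between 52.7% and 63.4%, depending on where the patient falls and whether none or half of the risk is retained. Across trials, at low exit rates, the change is a few points or less. Both statements assume that 4.11 is followed and the leaver is scored as a non-DLT.

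Two stronger readings are not supported. A reader might infer that 91/49/17% is wrong. It is arithmetically correct when every counted patient carries full-window risk, and it ceases to apply only when that fails. A reader might also infer that the plan expressly scores early leavers as DLT-free. It makes them evaluable and does not replace them, which implies that scoring, but no passage states it.

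**What to change.** Reconcile 4.1, 4.3, 4.11 and 9 with one definition for escalation and MTD decisions. A patient is DLT-evaluable if either:
- a DLT occurred at any time in the window; or
- the patient received a sponsor-prespecified minimum of the planned week −2 to induction treatment, including BCG, and was observed to the end of the nine weeks.

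Other early leavers are replaced. The same condition applies to the first three patients, the added three, any re-opened level and the six patients in the MTD rule. Keep the at-least-one-dose set for the safety tables.

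The cost is amendment wording and an occasional replacement. At one patient every two to three months (Section 3) plus the nine-week window (about 2.1 months), a replacement could delay a cohort's decision by up to about four to five months. The 27-for-24 allowance should normally be enough, given step 5. However, Section 4.1 still states a maximum of 18 evaluable subjects, and the note in Section 4.3 still treats level 3 as the top level. Both must be reconciled with the four-level, 24-evaluable design in the same amendment.

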5 STUDY PROCEDURES

Table 5: Study Procedures

Timeline	Baseline	Treatment Period			Off Treatment	
	Screening ²	Pre-induction Phase (Day -14)	Induction Phase (weeks 0 thru 5)	Maintenance Phase: (weeks 7 thru 53)	End of Treatment Visit ²⁰	Follow-up ²¹
Assessments/Procedures	X		X	X		
Informed Consent	X					
History	X					
Physical exam ¹	X		X	X	X	
Concomitant meds	X	X	X	X	X	
ECOG Status	X	X	X	X	X	
Adverse events ³	X	X	X	X		X
Cystoscopy ⁴	X			X ^{4, 5}		
Urine cytology ⁴	X			X ⁴		
Imaging studies ⁶	X					
CBC with diff ⁷	X	X	X ⁷	X ⁷		
Chemistry labs ⁸	X	X	X	X ⁸		
Coagulation labs ⁹	X					
Thyroid tests ¹⁰	X			X ¹⁰		
Urinalysis	X		X	X	X	
Pregnancy test ¹¹	X					
Urine creatinine ¹²		X	X	X		
Urine PK sample ¹³		X	X			
Serum PK sample ¹⁴		X	X			
Research blood sample ¹⁵		X ¹⁵	X ¹⁵	X ¹⁵		
Research urine sample ¹⁶		X ¹⁶	X ¹⁶	X ¹⁶		
Tissue for research ¹⁷	X			X		
Pembrolizumab ¹⁸		X	X	X		
BCG ¹⁹			X	X		
Survival/disease status						X

- Physical exam will include weight and vital signs (temperature, pulse, and blood pressure). Height will be measured at baseline only. A full physical exam should be performed at baseline; thereafter, a directed physical may be performed prior to each treatment administration.

2. Screening labs should be completed within 14 days prior to registration (except for pregnancy test). All other screening assessments should be performed with 28 days prior to registration unless otherwise noted. Screening and pre-induction procedures may be performed on the same day, if desired.
3. Baseline symptoms should be recorded at screening.
4. Cystoscopies will be performed at baseline and then to check for recurrence at weeks 17, 25, 33, 41, and 49; these may be performed more often if clinically indicated. A urine cytology will be performed at the same time as each cystoscopy.
5. Treatment of patients who undergo biopsy for pathogenic response at weeks 17, 25, 33, 41, and 49 may be held for the outcome at discretion of the treating surgeon.
6. Only required for patients who are positive for invasion. Baseline imaging will consist of CT or MRI. Studies showing normal upper tracts and absence of locally advanced bladder cancer required within 60 days before study registration. Follow-up imaging is not required but may be performed if clinically indicated.
7. CBC will be performed at baseline pre-dose at each treatment visit, within 48 hours if necessary. CBC may be performed more often if clinically indicated.
8. Chemistry labs will be done at baseline and pre-dose at each treatment visit and should include albumin, alkaline phosphatase, ALT/AST, lactate dehydrogenase, bicarbonate, creatinine (or calculated creatinine clearance), uric acid, calcium, chloride, glucose, phosphorus, potassium, sodium, magnesium, bilirubin, total protein, BUN. Chemistry labs may be completed within 48 hours prior to dosing.
9. Includes PT/INR, PTT
10. Includes T3, FT4, and TSH and will be performed at screening and week 17 only (unless otherwise clinically indicated).
11. Serum or urine pregnancy test required within 7 days prior to Day -14 for all females of child-bearing potential.
12. A portion of each urine sample will be sent to the NMH Labs for urine creatinine measurement
13. **For first 3 patients only:** A urine sample for PKs will be collected prior to dosing and 2 hours (+/- 5 minutes allowed for collections) after dosing at weeks -2 and 4. Urine samples for PK testing will be banked and stored in the [name] Lab for future analysis. See Section 8 and the Lab Manual for details.
14. **For first 3 patients only:** Serum concentrations of MK-3475 will be evaluated during pre-induction (week -2) and during induction (week 4). For each sample 3 mL of whole blood will be collected in a red top tube (containing now anti-coagulant or serum separator gel) just prior to dosing (time 0) and at 15, 30, and 60 minutes (+/- 2 minutes) post-dosing. See Section 8 and Lab Manual for processing and shipping details.
15. A separate blood sample for measurement of cytokines and cellular profiling by flow cytometry will be collected at weeks -2, 0, and 17. Two 3 ml lavender EDTA tubes should be collected pre-dose at each time-point. Tubes will be transported to the Pathology Core Facility for processing and distribution to the Flow Cytometry Core Laboratory of the Lurie Cancer Center (for flow studies) and Myriad Laboratories (for cytokine assays). Please refer to Section 8.0 and the corresponding lab manual for additional instructions. A portion of the blood specimens that have been collected for cytokine analysis may be used in plasma PK assays, per Principal Investigator discretion.
16. Urine for sample (approximately 40-50 ml) for measurement of cytokines and cellular profiling by flow cytometry will be also be collected in a sterile cup throughout treatment, prior to dosing and an optional collection at the third void approximately 4-6 hours after each dose (weeks -2, 0, 1, 2, 3, 4, 5, 7, 9, 11, 13, 15, 17, 21, 25, 29, 33, 37, 41, 45, and 49). *NOTE: The first void will be 2 hours post-dosing as part of the treatment (may be used for PK sampling if participating in that component), the second void after dosing will not be used for any correlative studies and should be discarded. An optional urine for research will be obtained at the third void, which is typically 4-6 hours after dosing; however the time does not need to be exact and may be adjusted depending on patient needs/urgency.*

Urine will be collected in a sterile plastic container and transported to the Pathology Core Facility for processing. The cell pellets will then be sent to the Flow Cytometry lab for flow studies; the supernatant will be sent to Myriad Laboratories for cytokine analysis. See section 8.0 and the Lab Manual for additional details.

17. Archived tumor tissue for biomarker analysis and NGS is requested for all patients. A formalin fixed paraffin embedded tumor tissue sample (or newly obtained formalin fixed biopsy of a tumor lesion not previously irradiated) may be provided in the form of at least fifteen unstained slides (5 slides for IHC analysis and 10 slides for whole exome sequencing). A cytologic specimen will not be acceptable. In addition, if biopsies are performed during scheduled cystoscopies throughout the study, an additional 15 unstained slides from each will also be obtained for study purposes only if the samples contain tumor tissue. See section 8.0 and the Lab Manual for details.
18. Pembrolizumab will be administered intravesically at the assigned dose for the cohort at the following weeks: -2, 0, 2, 4, 7, 9, 11, 13, 15, 17, 21, 25 29, 33, 37, 41, 45 and 49.
19. BCG 50 mg will be administered intravesically during induction (6 weekly doses) and maintenance (weeks 7, 9, 11, 13, 15, 17, 21, 25 29, 33, 37, 41, 45 and 49); every effort should be made to administer doses on the same day each week, however a window of +/-2 days is permitted for each dose.
20. Whether a patient completes the full year of therapy or discontinues early for any reason, an end-of-treatment visit should be conducted approximately 30 days (\pm 7 days) from the last dose of study drug.
21. Once off treatment, patients will be followed clinically for disease recurrence and survival according to the following schedule. After the last dose of trial therapy, follow patients every 3 months (\pm 30 days) during years 1 and 2, every 4 months (\pm 60 days) during years 3 and 4, every 6 months (\pm 60 days) during years 5 and 6, and every 12 months (\pm 90 days) thereafter, or until death, withdrawal, or end of study (whichever occurs first). If a patient discontinues treatment (for any reason other than disease recurrence) prior to completing the full year of therapy, they will immediately enter into the clinical follow-up phase.

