4 TREATMENT PLAN

4.1 Overview

Treatment will be administered on an outpatient basis. Treatment will be divided into pre-induction, induction and maintenance therapy phases. Two weeks prior to induction, subjects will receive the first intravesical instillation of pembrolizumab (week -2). During induction therapy, patients will receive standard intravesical instillation with BCG once weekly for 6 weeks (total of 6 BCG instillations). Patients will also be treated with concomitant pembrolizumab, given intravesically every 2 weeks during the induction period (total of 3 pembrolizumab instillations; weeks 0, 2, and 4). The maintenance phase starts at week 7 and continues up to 1 year (last dose and cystoscopy at week 49). Intravesical BCG and intravesical pembrolizumab will be given every 2 weeks for the first 12 weeks of maintenance therapy (weeks 7, 9, 11, 13, 15, 17 for a total of 6 doses) and then every 4 weeks thereafter (weeks 21, 25, 29, 33, 37, 41, 45 and 49 for a total of 8 doses) until completion of treatment or early discontinuation for any reason.

Cystoscopies will be performed 8 weeks (approximately 2 months) from the end of the induction period (week 17) and will be repeated at 8-week intervals until week

NU Study Number: NU 15U06
Merck Study Number: 3475-265

49. If ambulatory cystoscopy reveals any abnormal finding requiring further investigation, BCG and/or pembrolizumab administration will be suspended until clinical investigation is completed. Tumor progression will be defined as positive transurethral resection and/or biopsy including tumor stage progression, muscle infiltration or metastasis. Should a bladder cancer progression be confirmed, the subject will be off treatment and off-study. Otherwise, subject will be able to resume study treatments approximately 4 weeks (per PI discretion) after any bladder biopsy to allow appropriate healing. NOTE: the PI will review and confirm when appropriate healing has occurred to allow resumption of treatment. Any patient who has a high-risk lesion resected on a follow-up cystoscopy must be removed from study treatment.

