4.5.3 Overview of Guidelines for Managing Suspected Pneumonitis from pembrolizumab

Subjects with symptomatic pneumonitis should immediately stop receiving pembrolizumab and have an evaluation. The evaluation may include bronchoscopy and pulmonary function tests to rule out other causes such as infection. If the subject is determined to have study drug associated pneumonitis, the suggested treatment plan is detailed in the table below.

Table 4-6: Management of Pneumonitis		
Study drug associated pneumonitis	Withhold/Discontinue pembrolizumab?	Supportive Care
Grade 1 (asymptomatic)	No action	Intervention not indicated
Grade 2	Withhold pembrolizumab, may return to treatment if improves to Grade 1 or resolves within 2 weeks	Systemic corticosteroids are indicated. Taper if necessary.
Grade 3 and Grade 4	Discontinue pembrolizumab	Systemic corticosteroids are indicated. The use of infliximab may be indicated as appropriate. Refer to the Event of Clinical Interest and Immune-related Adverse Event Guidance Document for additional recommendations.

For Grade 2 pneumonitis that improves to \leq Grade 1 within 2 weeks, the following rules should apply:

First episode of pneumonitis

- May increase dosing interval by one week in subsequent cycles
- Second episode of pneumonitis – permanently discontinue pembrolizumab if upon rechallenge subject develops pneumonitis \geq Grade 2

4.5.4 Supportive Care Guidelines for Events of Clinical Interest and Immune-related Adverse Events (irAEs)

Events of clinical interest of a potential immunologic etiology (irECIs) may be defined as an adverse event of unknown etiology, associated with drug exposure and is consistent with an immune phenomenon. irAEs may be predicted based on the nature of the pembrolizumab compound, its mechanism of action, and reported experience with immunotherapies that have a similar mechanism of action. Special attention should be paid to AEs that may be suggestive of potential irAEs. An irAE can occur shortly after the first dose or several months after the last dose of treatment.

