4.9 Duration of Follow Up

4.9.1 Safety Follow-Up Visit

The end-of-treatment visit will be conducted approximately 30 days (\pm 7 days) after the last dose of trial treatment, OR at the time of the week 53 cystoscopy (if the patient completes all of the maintenance phase), OR before the initiation of a new anti-cancer treatment, whichever comes first. All AEs that occur prior to this visit should be recorded. Subjects with an AE of Grade > 1 will be followed until the resolution of the AE to Grade 0-1 or until the beginning of a new anti-neoplastic therapy, whichever occurs first. SAEs that occur within 90 days of the end of treatment or before initiation of a new anti-cancer treatment should also be followed and recorded.

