6.5 Events of Clinical Interest

Selected non-serious and serious adverse events are also known as Events of Clinical Interest (ECI) and must be recorded as such on the Adverse Event case report forms/worksheets and reported within 24 hours to the QAM within 2 working days to Merck Global Safety (as outlined in 6.7.5).

Events of clinical interest for this trial include:

1. an overdose of Merck product.
2. an elevated AST or ALT lab value that is greater than or equal to 3X the upper limit of normal and an elevated total bilirubin lab value that is greater than or equal to 2X the upper limit of normal and, at the same time, an alkaline phosphatase lab value that is less than 2X the upper limit of normal, as determined by way of protocol-specified laboratory testing or unscheduled laboratory testing.*

***Note:** These criteria are based upon available regulatory guidance documents. The purpose of the criteria is to specify a threshold of abnormal hepatic tests that may require an additional evaluation for an underlying etiology. .

3. In the event a subject develops any of the following AEs, a detailed narrative of the event should be reported as an ECI to the Sponsor within 24 hours and to Merck Global Safety within 2 working days of the event:
 - a. Grade \geq 3 diarrhea
 - b. Grade \geq 3 colitis
 - c. Grade \geq 2 pneumonitis
 - d. Grade \geq 3 hypo- or hyperthyroidism

A separate guidance document has been provided entitled "event of Clinical Interest and Immune-Related Adverse Event Guidance Document." This document provides guidance regarding identification, evaluation and management of ECIs and irAEs. Additional ECIs are identified in this guidance document and also need to be reported to the QAM within 24 hours and to Merck Global Safety within 2 working days of the event.

Subjects should be assessed for possible ECIs prior to each dose. Lab results should be evaluated and subjects should be asked for signs and symptoms suggestive of an immune-related event. Subjects who develop an ECI thought to be immune-related should have additional testing to rule out other etiologic causes. If lab results or symptoms indicate a possible immune-related ECI, then additional testing should be

NU Study Number: NU 15U06
Merck Study Number: 3475-265

performed to rule out other etiologic causes. If no other cause is found, then it is assumed to be immune-related.

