ECIs that occur in any subject from the date of first dose through 90 days following cessation of treatment, or the initiation of a new anticancer therapy, whichever is earlier, whether or not related to the Merck's product, must be reported within 24 hours to the QAM and to Merck Global Safety within 2 working days.

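### Scheduled thyroid tests stop at week 17 and no blood test is scheduled after the last dose, short of the protocol's own 90-day safety window

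*Combined protocol and SAP*

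**What the plan says.** **Testing schedule (section 5, Table 5 and footnotes)**
- Thyroid, footnote 10: "Includes T3, FT4, and TSH and will be performed at screening and week 17 only (unless otherwise clinically indicated".
- Chemistry, footnote 8: "Chemistry labs will be done at baseline and pre-dose at each treatment visit". The panel includes ALT/AST, bilirubin, alkaline phosphatase, creatinine and glucose, and may be taken up to 48 hours before dosing.
- CBC, footnote 7: "CBC will be performed at baseline pre-dose at each treatment visit, within 48 hours if necessary".
- The End of Treatment Visit column marks urinalysis but no CBC, chemistry or thyroid test. Section 4.9.1, which describes that visit, adds none. Footnote 20 places it about 30 days after the last dose, for early stoppers as well as completers.

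**Dosing (section 4.1)**
- After week 17, BCG and pembrolizumab continue at "weeks 21, 25, 29, 33, 37, 41, 45 and 49 for a total of 8 doses".

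**Safety windows**
- Section 6.5 requires reporting of "ECIs that occur in any subject from the date of first dose through 90 days following cessation of treatment", or until new anticancer therapy if that is earlier.
- Section 6.5 also says: "Subjects should be assessed for possible ECIs prior to each dose. Lab results should be evaluated". Its list of events of clinical interest (ECIs) includes a combined AST/ALT, bilirubin and alkaline phosphatase criterion, and thyroid disorder of Grade 3 or higher.
- Section 4.5.4 on immune-related adverse events (irAEs): "An irAE can occur shortly after the first dose or several months after the last dose of treatment".
- Section 4.9.1, on the end-of-treatment visit: "All AEs that occur prior to this visit should be recorded". Section 6.1 sets the general adverse-event window at 30 days after cessation.

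**The concern.** The protocol names events that are found wholly or partly from blood tests, says when they can occur, and sets a period in which they must be reported. The testing schedule does not span that period. A thyroid change that starts after week 17, or a liver, renal, glucose or blood-count change that starts after the last pre-dose sample, is seen only if something prompts a test. An event without symptoms prompts nothing.

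What is at stake is the secondary objective in section 2.2.2: the number, frequency and severity of adverse events. Section 1.3.1 says that no study has addressed the safety of a PD-1 antibody given intravesically, and section 4.5.1 predicts that immune-related events will be rare by this route. Missing silent events pulls the result toward that prediction. It also delays detection of events for which Table 4-4 prescribes a response.

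**Working it through.** No power or error-rate figure bears on this point. The check is a count of doses and weeks against the stated windows.

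**1. Doses.** From section 4.1 and Table 4-1: 1 (week -2) + 3 (weeks 0, 2, 4) + 6 (weeks 7 to 17) + 8 (weeks 21 to 49) = 18 pembrolizumab doses. The 8 after week 17 reproduces the protocol's own count.

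**2. Treatment visits with CBC and chemistry.** 1 (week -2) + 6 (weeks 0 to 5) + 6 (weeks 7 to 17) + 8 (weeks 21 to 49) = 21. Every visit has a pre-dose sample, so each dose except the last is followed by a later scheduled sample.

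**3. Thyroid gap, for a patient who completes treatment.**
- Week 17 to the last dose: 49 - 17 = 32 weeks.
- To the end of the 30-day adverse-event window: 32 + 30/7 = 36.3 weeks (254 days).
- To the end of the 90-day ECI window: 32 + 90/7 = 44.9 weeks (314 days).
- Whole window, first dose to day 90: 49 - (-2) + 90/7 = 63.9 weeks. Share without a scheduled thyroid test: 44.9 / 63.9 = 70%.
- Sensitivity: section 4.8 gives week 47 for the last dose, against week 49 in section 4.1, Table 4-1 and footnote 18. These must be reconciled. With week 47 the gap is 30 + 12.9 = 42.9 weeks of 61.9, or 69%, so the result does not depend on which stands.

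**4. CBC and chemistry gap.** The last scheduled sample precedes the last dose, so none of the following 90 days has one (up to 92 days with the 48-hour allowance). As a share of the whole window this is 12.9 / 63.9 = 20%, all of it after treatment. The Maintenance column of Table 5 is headed weeks 7 to 53, but footnotes 7 and 8 tie these tests to treatment visits, the last of which is week 49.

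**5. Early stoppers.** A patient who stops before week 17 has no scheduled thyroid test after baseline.

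**6. Scale of one missed patient.** With the maximum of 24 evaluable patients in section 9, one patient with an undetected event moves a reported proportion by 1/24 = 4.2 percentage points. The documents give no rate for silent events, so no expected number can be calculated.

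**7. What an end-of-treatment sample would cover.** At day 30 (±7 days) it falls close to the end of the adverse-event window. It leaves 90 - 30 = 60 days of the ECI window (53 to 67) without a scheduled test.

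**The case against.** The case for the current schedule has real force.

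- **On-treatment cover is good.** Liver, renal, glucose and blood-count changes are measured before every dose to the end of treatment. A reader might infer that laboratory surveillance as a whole stops long before the risk window ends, or that 70% describes all laboratory tests. The documents do not support either: both apply to thyroid tests only.
- **Other routes to detection exist.** Footnote 10 allows clinically indicated tests. The liver ECI accepts unscheduled results. Section 6.5 asks about symptoms before each dose, and section 4.9.1 follows adverse events above Grade 1 to Grade 0-1 or new anti-neoplastic therapy. This stands, and it limits the loss to silent change that first appears after the last scheduled test.
- **The thyroid ECI is Grade 3 or higher**, and Table 4-4 leaves pembrolizumab unchanged for several thyroid grades. This lowers the clinical weight, but section 2.2.2 counts adverse events of any severity.
- **The 90-day rule is a reporting rule**, not a promise of sampling, and the word only in footnote 10 is a deliberate choice. So this is a mismatch between schedule and purpose rather than a contradiction in terms.
- **Low systemic exposure is expected.** Section 1.3.1 argues that the urothelium is unlikely to let the antibody through, but adds that inflammation from BCG may raise permeability. That is a reason to measure.

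A reader might also infer, from the empty adverse-event cell at the end-of-treatment visit in Table 5, that adverse events are not collected there. Sections 4.9.1 and 6.1 already require their recording to about that visit, so the cell is at most a table inconsistency.

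**Conclusion.** The point holds for scheduled tests. Thyroid function has no scheduled test across the last 8 dosing visits and the period after them: 44.9 weeks, or 70% of the window from first dose to day 90. CBC and chemistry are adequate during treatment and have no scheduled test in the 90 days after it. Silent events in those periods can go unrecorded, and the bias in the descriptive safety summary is toward fewer events.

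The figures assume the full 18-dose course, a last dose at week 49, and no new anticancer therapy within 90 days. Earlier therapy shortens the ECI window. The reading of Table 5 comes from extracted text in which columns may have shifted, but footnotes 7, 8 and 10 support it independently.

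A reader might infer that dose finding is compromised. It is not: the DLT period covers pre-induction and induction (section 4.3.1), and on the planned course both gaps open after it. The MTD is unaffected, and the affected analysis is descriptive. The point merits an amendment but does not threaten the primary objective.

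**What to change.** 1. In Table 5, mark CBC, chemistry and thyroid tests in the existing End of Treatment Visit column. This gives every patient one sample after the last dose, close to the end of the adverse-event window, and gives those who stop before week 17 a thyroid result after baseline.
2. Reconcile footnote 10 with section 6.5, so that thyroid function is also checked during maintenance after week 17, on blood already drawn before dosing. The sponsor should set the interval; the documents give no basis for particular weeks.
3. State that laboratory detection in the remainder of the 90-day ECI window relies on clinically triggered tests, so that the safety report can say so.

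Cost: one extra blood draw at a visit that already takes place, a few added assays per patient, and some incidental low-grade abnormalities to follow. No new visit is needed.
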